7.3 Phase II

7.3.1 Dose Delays/Modifications

7.3.1.2. Immune checkpoint inhibitor(s)

Use of immune checkpoint inhibitor(s), such as durvalumab, in the post-chemoradiation consolidation period is at the discretion of the treating physician.

7.3.2 Treatment Delay

Treatment delay of immune checkpoint inhibitor will follow standard practice in managing toxicities attributed to immune checkpoint inhibitor or for other reasons (scheduling preference, etc). No dose reductions are allowed.

Treatment with nintedanib/placebo has to be interrupted in case **ANY** of the criteria listed below is fulfilled.

- Nausea of CTCAE Grade ≥ 3 , despite supportive care
- Vomiting of CTCAE Grade ≥ 2 , despite supportive care
- Diarrhea of CTCAE Grade ≥ 2 for more than 3 consecutive days, despite supportive care
- AST and/or ALT of CTCAE Grade ≥ 2 in conjunction with bilirubin of CTCAE Grade ≥ 1
- AST and/or ALT of CTCAE Grade ≥ 3

- Other non-hematological adverse event of CTCAE Grade ≥ 3 considered drug-related
- Neutropenia and fever $> 38.5^{\circ}\text{C}$
- Neutropenia CTCAE Grade 4 for more than 7 days, without fever
- Platelets $< 25,000\text{mm}^3$, with or without bleeding
- Grade > 2 proteinuria

7.3.4 Dose Reduction

As initial measure for the management of side effects, treatment with nintedanib/placebo should be temporarily interrupted until the specific adverse reaction has resolved to levels that allow continuation of therapy. Nintedanib/placebo treatment may be resumed at a reduced dose. Dose adjustments in 100 mg steps per day (i.e., a 50 mg reduction per dosing) based on individual safety and tolerability are recommended. In case of further persistence of the adverse reaction(s), i.e., if a patient does not tolerate 100 mg twice daily, treatment with nintedanib will be discontinued.

The following dose levels will be used in case dose adjustments are required for management of undue toxicity:

Table 3 Nintedanib/Placebo Dose Reduction

Dose Level	Dose
-2	100 mg BID
-1	150 mg BID
1 (Starting Dose)	200 mg BID

7.3.5 Management of Adverse Events

Table 4 Recommended Dose Adjustments for Nintedanib

CTCAE Adverse Reaction	Dose Adjustment
Diarrhea \geq Grade 2 for more than 7 consecutive days, despite anti-diarrheal treatment** OR Diarrhea \geq Grade 3, despite anti-diarrheal treatment**	1st Episode Reduce dose from 200 mg BID to 150 mg BID
Vomiting ** \geq Grade 2 AND/OR Nausea \geq Grade 3, despite anti-emetic treatment**	2nd Episode Reduce dose from 150 mg BID to 100 mg BID
AST and/or ALT elevations Grade 2 in conjunction with bilirubin of \geq Grade 1 OR AST and/or ALT elevations of \geq Grade 3	3rd Episode Stop treatment
Other non-hematological or hematological adverse reaction of \geq Grade 3	

** See Section 7.4 for additional guidelines.

If nintedanib will be combined with compounds that are solely metabolized by the liver and/or induce liver enzyme elevations, both molecules should be reduced in case of liver enzyme elevations according to the defined dose reductions for nintedanib/placebo as mentioned above and for the other compound as mentioned in their prescribing information.

7.4 General Concomitant Medication and Supportive Care

7.4.1 Diarrhea

Diarrhea was the most frequently reported GI event and appeared in close temporal relationship with the administration of docetaxel in the clinical trial LUME-Lung 1. The majority of patients had mild to moderate diarrhea, 6.3% of the patients had diarrhea of Grade ≥ 3 in combination treatment compared to 3.6% treated with docetaxel alone. Diarrhea should be treated at first signs with adequate hydration and anti-diarrheal medicinal products (e.g., loperamide), and may require interruption, dose reduction or discontinuation of therapy with nintedanib/placebo.

7.4.2 Nausea and Vomiting

Nausea and vomiting, mostly of mild to moderate severity, were frequently reported gastrointestinal adverse events in the clinical trial LUME-Lung 1. Interruption, dose reduction or discontinuation of therapy with nintedanib/placebo may be required despite appropriate supportive care. Supportive care for nausea and vomiting may include medicinal products with anti-emetic properties, e.g., glucocorticoids, anti-histamines or 5-HT₃ receptor antagonists and adequate hydration.

In the event of dehydration, administration of electrolytes and fluids is required. Plasma levels of electrolytes should be monitored, if relevant GI adverse events occur. Participants may be pretreated for nausea and vomiting with appropriate anti-emetics as clinically indicated.

7.4.3 Neutropenia and Sepsis

A higher frequency of neutropenia of CTCAE Grade > 3 was observed in patients treated with nintedanib in combination with docetaxel as compared to treatment with docetaxel alone in the clinical trial LUME-Lung 1. Subsequent complications such as sepsis or febrile neutropenia have been observed.

7.4.4 Hepatic Function

The safety and efficacy of nintedanib has not been studied in patients with moderate (Child Pugh B) or severe (Child Pugh C) hepatic impairment. Therefore, treatment with nintedanib is not recommended in such patients.

Administration of nintedanib was associated with an elevation of liver enzymes (i.e., ALT, AST, ALKP (alkaline phosphatase), and bilirubin), with a potentially higher risk for female patients.

These increases were reversible in the majority of cases and not associated with clinically manifest liver disorders. Hepatic transaminases, ALKP and bilirubin levels are recommended to be closely monitored after start of therapy with nintedanib.

If relevant liver enzyme elevations are measured, interruption, dose reduction or discontinuation of the therapy with nintedanib/placebo may be required. Refer to **Appendix B** for guidelines in the recognition and approach to drug-induced liver injury.

7.4.5 Other

Additional chemo-, immuno-, biologic therapies are not allowed during the active treatment period of this trial. Hormone-related therapies (e.g., adjuvant aromatase inhibitors, etc) are permitted if patients have been on these for more than one month prior to initiation of study protocol. Palliative radiotherapy may be permitted for symptomatic control of pain from bone metastases in extremities after discussion with the Principle Investigator. Patients who develop new/worsening brain metastases within the study treatment period may continue on protocol and receive palliative WBRT (or gamma-knife radiosurgery as clinically indicated). Nintedanib/placebo treatment will be temporarily interrupted while undergoing palliative therapy for brain metastases. If such patient does not have disease progression elsewhere, development of brain metastasis will not be considered a disease-progression event (clarification for purposes of secondary objective analysis).

If co-administered with nintedanib strong P-gp inhibitors (e.g., ketoconazole or erythromycin), may increase exposure to nintedanib. In such cases, patients should be monitored closely for tolerability of nintedanib. Management of side effects may require interruption, dose reduction or discontinuation of therapy with nintedanib/placebo.

Strong P-gp inducers (e.g., rifampicin, carbamazepine, phenytoin, and St. John's Wort) may decrease exposure to nintedanib. Co-administration with nintedanib/placebo should be carefully considered.

7.6 Treatment Discontinuation

Upon treatment discontinuation all end of treatment evaluations and tests will be conducted. All participants who discontinue due to an AE must be followed until the event resolves or stabilizes. Appropriate medical care should be provided until signs and symptoms have abated, stabilized, or until abnormal laboratory findings have returned to acceptable or pre-study limits. The final status of the AE will be reported in the participant's medical records and the appropriate eCRF.

Reasons for treatment discontinuation should be classified as follows:

- Death

- Progressive disease warranting either initiation of systemic chemotherapy or hospice care
- Toxicity; related or unrelated toxicity
- Investigator judgment
 - The Investigator may discontinue a participant if, in his/her judgment, it is in the best interest of the participant to do so.
- Noncompliance
- Participant voluntary withdrawal
 - A participant may withdraw from the study at any time, for any reason. If a participant discontinues treatment, an attempt should be made to obtain information regarding the reason for withdrawal.
- Sponsor decision.

7.7 Compliance

Patients will be provided a pill diary to record each dose of nintedanib/placebo (date, time, number of capsules) taken. A pill count will be performed at each subsequent clinic visit/evaluation.

8 INVESTIGATIONAL PRODUCT

8.1 Drug Shipment

Nintedanib/placebo will be provided by Boehringer Ingelheim and shipped to the participating sites.

The date of receipt, of the shipment, and the amount of drug received will be documented. Drug shipment records will be retained by the investigational pharmacist or designee.

8.2 Pharmaceutical information

8.2.1 Nintedanib - Study Drug

Substance (INN):	Nintedanib
Pharmaceutical Form:	Soft gelatine capsule
Pharmaceutical Code	BIBF1120
Source:	Boehringer Ingelheim Pharma GmbH & Co. KG
Unit Strength:	100 mg and 150 mg capsules
Daily Dose:	Dose escalation portion: dose according to dose level assigned. During Phase II randomized study: 200 mg orally twice daily (without durvalumab) or dose determined from dose escalation portion in combination with durvalumab. Dose reduction according to Section Error! Reference source not found.
Duration of Use:	Continuous daily dosing until progression of disease (see exception regarding brain metastases in Section 7.3.5) or until criteria for interruption of treatment is met. The maximum time on treatment will be 6 months.
Route of Administration:	Oral
Posology:	Twice daily (to be swallowed whole, with a glass of water of about 250 mL with a dose interval of around 12 hours at the same times every day, usually in the morning and the evening after food intake)

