Objectives	
Primary:
 
 Phase 1: To evaluate the safety of the combination of durvalumab with nintedanib in patients with unresectable Stage II/III/oligometastatic IV NSCLC Phase 2: To compare the rate of symptomatic radiation pneumonitis at 6 months after completion of chemoradiation in patients with unresectable Stage II/III/oligometastatic IV NSCLC who completed chemoradiation followed by nintedanib versus placebo. 
Secondary:
 
 To compare the quality of life (QOL) in patients who received nintedanib versus placebo during active treatment until 6 months after completion of treatment. To compare the progression-free survival, overall survival and 1-year progression-free survival rate in patients who received nintedanib versus placebo. To compare pulmonary function test (PFT) results and RP score in patients who received nintedanib versus placebo. To compare the composite index (based on PFT, RP score and QOL) at the end of active treatment and 6 months after completion of treatment between patients who received nintedanib versus placebo. 
Exploratory:
 
 To investigate blood-based biomarkers in evaluating risk of developing radiation pneumonitis as well as the efficacy of nintedanib.
Study Design	
A Phase II, randomized, double-blind, placebo-controlled study of nintedanib as prophylaxis against radiation pneumonitis in patients with advanced NSCLC.
 
Addition of Phase I: With the November 2018 amendment allowing immune checkpoint inhibitor such as durvalumab consolidation therapy, a conventional dose-escalation design will be explored for patients who will be receiving durvalumab. Patients enrolled in the dose-escalation portion must commence nintedanib dosing at the same time as durvalumab is started. Dosing with nintedanib will start at 100 mg BID (see Table 1).

	
For patients who will be receiving durvalumab as standard of care prior to establishment of the recommended phase II dose of this combination, they will NOT undergo randomization (i.e. not blinded to treatment) and will receive active drug (nintedanib) on the first day of the first dose of durvalumab 10mg/kg every 2 weeks for up to 12 months.

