5 STUDY DESIGN

A maximum of 18 participants will be enrolled to the Phase I non-randomized dose escalation portion of this study. See Figure 1 for the Phase 1 dose-escalation study schema.

A maximum of 99 participants will be enrolled to the randomized Phase II, double-blind, placebo-controlled portion of the study of nintedanib as prophylaxis against radiation pneumonitis in patients with advanced NSCLC. The study schema is depicted below.

[figure not shown]
All participants will sign an informed consent prior to study related tests. All participants will meet the inclusion and exclusion criteria summarized in **Section 6.1** and **Section 6.2**.

Figure 1 Phase 1 Dose-escalation Study Schema

For patients who will be receiving durvalumab consolidation treatment as standard of care prior to establishment of the recommended phase II dose of this combination, they will NOT undergo randomization (i.e. not blinded to treatment) and will receive active drug (nintedanib) on the first day of the first dose of durvalumab 10mg/kg every 2 weeks for up to 12 months.

Figure 2. Phase II Study Schema

§Patients will be stratified according to chemotherapy regimen (i.e., platinum with etoposide, platinum with taxane, platinum with pemetrexed) utilized concurrently with radiation as well as exposure to immune checkpoint inhibitor therapy.

§§An interim analysis for futility will be conducted when the first $n_1=33$ patients have completed 6-months of follow-up post-chemoradiation; that is, when the first $n_1=33$ patients are evaluable for the primary end-point (the rate of CTCAE Grade 2 or higher radiation pneumonitis at 6

months after completion of chemoradiation). If the estimated common odds ratio (COR) is greater than or equal to 0.8, then the study will stop early for futility. Otherwise, the study will continue and enroll an additional $n_2=66$ patients. Additionally, at this time the safety profile of the treatment arms may be evaluated and considered in the decision for study continuation.

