6.2 Exclusion Criteria

- 1 WBRT < 14 days from the anticipated start of nintedanib/placebo administration.
- 2 Squamous cell NSCLC

- 3 Unable to start nintedanib/placebo treatment between 4 – 8 weeks after completing the last dose of thoracic radiation.
- 4 Active untreated brain or leptomeningeal metastases. In patients with treated CNS metastases, eligible if symptoms controlled for at least 4 weeks. Dexamethasone allowed if total daily dose does not exceed 2 mg.
- 5 Major injuries or surgery (e.g., craniotomy) <28 days from the start of nintedanib/placebo administration. Wound should be healed prior to starting therapy.
- 6 Second malignancies are allowed as long as the disease does not require active treatment with concomitant systemic cytotoxic chemotherapy, investigational or biologic therapy (e.g., anti-CTLA4 or HER2 monoclonal antibodies). Hormone-related therapies (e.g., LHRH agonists, tamoxifen, etc.) are allowed.
- 7 Concurrent uncontrolled illness including, but not limited to, ongoing or active infection, symptomatic congestive heart failure, unstable angina pectoris, cardiac arrhythmia, or psychiatric illness/social situation that would increase the risk associated with study participation and/or limit compliance with study requirements.
- 8 Inability to swallow study medication.
- 9 Presence of active malabsorption disorder (e.g., flare episodes documented within the preceding 3 months, presence of symptoms requiring daily medications for control) or history of extensive small bowel resection.
- 10 Known bleeding or thrombotic diathesis.
- 11 History of arterial or venous thromboembolic event within 12 months prior to study participation.
- 12 Active hemoptysis or history of clinically relevant hemoptysis as determined by the treating physician. Patients who had history of transient minor hemoptysis after bronchoscopic biopsy are eligible unless deemed otherwise by the treating physician.
- 13 CTCAE Grade 2 or higher proteinuria.
- 14 Investigational agent administered < 28 days prior to treatment with nintedanib. Last dose of systemic chemotherapy administered < 14 days prior to treatment with nintedanib.
- 15 Known chronic active hepatitis B or hepatitis C. HIV-positive patients receiving or are candidates for antiretroviral therapy are also excluded.
- 16 Pregnancy or breast feeding. Female patients with child-bearing potential must have a negative pregnancy test (β -HCG test in urine or serum) prior to commencing study treatment.

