7 TREATMENT PLAN

7.1 Dosing and Administration

Treatment will be administered on an outpatient basis. Each cycle will be 28 days. Patients will be dispensed sufficient supply for at least 28 days or until their next scheduled visit. Reported adverse events (AEs) and potential risks are described in **Section 1.6**. Appropriate dose modifications are described in **Section Error! Reference source not found.**

With the November 2018 amendment allowing immune checkpoint inhibitor such as durvalumab consolidation therapy, a conventional dose-escalation design will be explored for patients who will be receiving durvalumab. Patients enrolled in the dose-escalation portion must commence nintedanib dosing at the same time as durvalumab is started. Dosing with nintedanib will start at 100 mg BID (see Table 1).

For patients who will be receiving durvalumab as standard of care prior to establishment of the recommended phase II dose of this combination, they will NOT undergo randomization (i.e. not blinded to treatment) and will receive active drug (nintedanib) on the first day of the first dose of durvalumab 10mg/kg every 2 weeks for up to 12 months.

All administered doses of the study drugs will be recorded in a pill diary to be provided to the patient (**Appendix E**).

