7.1.2 Durvalumab

During dose escalation, the first two doses of durvalumab (10 mg/kg) will be given intravenously (IV) every 2 weeks over 60 minutes. These doses will be administered together with Cycle 1 Day 1 and day 15 (-1/+7 days) doses of nintedanib. Subsequent doses will be administered according to institutional practice.

During phase II, use of an immune checkpoint inhibitor (durvalumab), in the post-chemoradiation consolidation period is at the discretion of the treating physician.

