7.2 Phase I

Dose escalation will proceed in a 3+3 fashion. Standard 3+3 rules will be followed until the maximum tolerated dose (MTD) is found. A total of 3 dose levels will be explored, with the MTD defined as the dose level wherein no more than 1 out of 6 patients evaluable for dose limiting toxicities (DLTs) experienced treatment-related DLT (Table 1).

Initially, 3 patients are enrolled at dose level 1. If no dose DLTs are observed, then 3 new patients are escalated to dose level 2. If ≥ 2 DLTs are observed at dose level 1, then dose-escalation stage is completed and study will be terminated.

If 1 DLT is observed, an additional 3 patients are enrolled at dose level 1. In those 6 patients at dose level 1, if ≤ 1 DLTs are observed attributable to the combination or nintedanib alone, we will proceed to dose level 2; otherwise, the study will be terminated if ≥ 2 DLTs are observed at dose level 1. If ≥ 2 DLTs are observed at dose level 2, the prior dose level (level 1) will be expanded to total of 6 patients if it has not been done yet. Otherwise, if 0-1 DLTs are observed at dose level 2, we proceed to dose level 3. The same basic principles are followed until the dose determined as the MTD is identified to use in Phase II.

Dose-limiting toxicities (DLTs) are as defined in Section 7.2.3. Once the MTD is determined, subsequent patients receiving durvalumab will be randomized to either nintedanib at MTD or placebo (Phase II). Nintedanib may also be started for subsequent patients at any time point (i.e. one or more durvalumab doses maybe given in the consolidation phase before protocol treatment is started) provided other eligibility criteria are met.

Table 1 Dose escalation scheme for the combination of nintedanib with durvalumab (Phase I)

Dose Level	Nintedanib Dose	Durvalumab dose
1	100 mg BID	10mg/kg every 2 weeks
2	150 mg BID	10mg/kg every 2 weeks
3	200 mg BID	10mg/kg every 2 weeks

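### The Phase II dose rule turns on durvalumab alone, so on a literal reading a patient on another checkpoint inhibitor who is allocated active drug starts at 200 mg BID

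*Combined protocol and SAP*

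**What the plan says.** **Dose.** Section 8.2.1 gives the Phase II active dose as "200 mg orally twice daily (without durvalumab) or dose determined from dose escalation portion in combination with durvalumab". Section 7.2 likewise applies the MTD only to patients on durvalumab. Table 3 in Section 7.3.4 lists 200 mg BID as the starting dose and mentions no checkpoint inhibitor.

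**Permitted agents, open wording.** Section 7.3.1.2, within the Phase II treatment plan, states: "Use of immune checkpoint inhibitor(s), such as durvalumab, in the post-chemoradiation consolidation period is at the discretion of the treating physician". Footnote 12 to Table 5 in Section 9.10 repeats this in nearly the same words.

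**Permitted agents, narrow wording.** Section 7.1.2 has the parallel sentence with a different scope: "During phase II, use of an immune checkpoint inhibitor (durvalumab), in the post-chemoradiation consolidation period is at the discretion of the treating physician". Section 13.1 equates immune therapy with durvalumab. Section 13.2 makes durvalumab patients eligible and leaves other immunotherapy agents to the future.

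**Entry to Phase II.** Section 13.3 says that escalation will not hold up patients who are not exposed to immunotherapy. Its explanatory clause then restates this as patients for whom durvalumab is not chosen, and requires only durvalumab patients to pass through escalation first.

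**Concomitant treatment.** Section 7.4.5 bars additional immunotherapy during active treatment and does not mention durvalumab.

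**Evidence with another agent.** Section 2 summarises a nintedanib and pembrolizumab escalation study: 13 enrolled, 12 evaluable for DLT, none with NSCLC, three liver-enzyme DLTs at 200 mg BID, and 150 mg BID recommended.

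**The concern.** The dose rule has two branches, with durvalumab and without it, while the Phase II permission in Section 7.3.1.2 covers a wider class. A patient on a different checkpoint inhibitor meets the second branch literally, although that branch was presumably written for patients on no checkpoint inhibitor at all.

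What is at stake is the starting dose of a blinded drug. Section 13.1 justifies escalation with durvalumab, starting at 100 mg BID, because that combination had not been tested in this setting. On the literal reading another agent would skip that step and go straight to the dose at which the Rationale reports liver toxicity with pembrolizumab.

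**Working it through.** The plan states no figure to reproduce. The check is mainly textual, with simple arithmetic for size.

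**1. Which text governs a Phase II patient on another checkpoint inhibitor?**

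| Section | Wording, in brief | Direction |
|---|---|---|
| 7.3.1.2 | Class permitted, durvalumab as an example | Open |
| 9.10, Table 5, footnote 12 | Same, but attached to the durvalumab row | Weakly open |
| 7.1.2 | Class identified with durvalumab | Durvalumab only |
| 13.1 | Immune therapy equated with durvalumab | Durvalumab only |
| 13.2 | Other agents in the future | Durvalumab only for now |
| 13.3, opening | Only patients not exposed to immunotherapy bypass escalation | Closed to other agents |
| 13.3, explanatory clause | Bypass if durvalumab is not chosen | Open |
| 7.4.5 | No additional immunotherapy | Depends on the meaning of additional |

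The synopsis and Section 7.1 also use the phrase such as durvalumab, but only in a lead-in that describes the amendment ("allowing immune checkpoint inhibitor such as durvalumab consolidation therapy, a conventional dose-escalation design will be explored for patients who will be receiving durvalumab"). The operative part concerns durvalumab patients in escalation. These two places are not Phase II permissions, and I give them no weight.

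Exclusion criterion 14 in Section 6.2 ("Investigational agent administered < 28 days prior to treatment with nintedanib") does not close the gap. It does not reach a marketed checkpoint inhibitor.

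**2. What dose follows?** Under Section 7.3.1.2 the agent is allowed. Under Section 8.2.1 the patient is without durvalumab. Under the explanatory clause of Section 13.3 no escalation step applies. Active drug therefore starts at 200 mg BID, as in Table 3.

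**3. Size of the dose gap.** 2 × 200 = 400 mg per day against 2 × 150 = 300 mg per day. The difference is 100 mg per day, and 400/300 = 1.33.

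**4. Strength of the pembrolizumab evidence.** The number treated at 200 mg BID is not given. Taking 3 to 12 patients as an assumed range, with each DLT in a different patient, the share is 3/12 = 25%, 3/9 = 33%, 3/6 = 50% or 3/3 = 100%. This trial's own escalation rule (Section 7.2) tolerates at most 1 in 6, or 17%. Three DLTs in six or fewer patients would fail that rule.

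**5. Number exposed.** With 1:2 allocation the share on active drug is 66/99 = 2/3. The number *k* of patients on another agent is unknown. For assumed *k* = 1, 3 or 6, the expected number starting active 200 mg BID is 0.7, 2 or 4. If other agents are in practice refused, it is zero.

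**The case against.** The strongest reply is that the intended meaning is clear. Only durvalumab has a dose and infusion schedule (Section 7.1.2 and Table 1), a row in Table 5 and a supply section (8.6). Sections 7.1.2, 13.1 and 13.2 all point to it. The natural meaning of additional immunotherapy in Section 7.4.5 is anything beyond the agent the protocol sets out, which admits durvalumab and excludes the rest. On that reading nobody is affected. Checkpoint-inhibitor exposure is also a stratification factor, so the agent should come to light at central randomisation. Liver-related entry limits (6.1), chemistry at each cycle (9.4), interruption and reduction rules (7.3.2, 7.3.5) and expedited liver reporting (11.3) limit harm.

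Most of this stands, and it is why durvalumab-only is the likely intent. It does not remove the contradiction. Section 7.3.1.2 still permits the wider class, and nothing says that Section 7.1.2 prevails. Section 13.2 gives no trigger for its future admission of other agents. The stratification factor may flag the agent but sets no dose, and the liver rules act after toxicity appears.

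A reader might argue that Section 7.4.5 must either bar durvalumab as well or let in every checkpoint inhibitor. The documents do not force that choice, because the middle reading above is available.

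A reader might also take the stratification wording ("utilized concurrently with radiation as well as exposure to immune checkpoint inhibitor therapy") as permission for other agents alongside nintedanib. It is not. The Rationale introduces the factor with reference to checkpoint inhibitors used as induction, with radiation or as consolidation, so it can record earlier exposure.

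**Conclusion.** The inconsistency is real and worth correcting, as a low-cost safety clarification. Section 7.3.1.2 opens the class, the dose rule in Section 8.2.1 recognises only durvalumab, and read together they give a starting dose one third above the one the protocol itself reports as recommended with pembrolizumab.

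Two stronger conclusions are not supported. One is that patients on other agents will receive 200 mg BID: the text allows this without requiring it, and several sections point the other way. The other is that 200 mg BID has been shown to be unsafe with checkpoint inhibitors in this population: the cited study was small, had no NSCLC patients and concerned one agent, and its denominator at 200 mg is not given.

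The number affected is unknown, probably small and possibly zero; the figures for *k* are assumptions. The primary test, its alpha and the sample size do not depend on this point.

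**What to change.** - **Section 8.2.1 and the starting dose in Table 3 (7.3.4):** 200 mg BID only when no checkpoint inhibitor is given concurrently; the Phase I dose with durvalumab.
- **Section 7.3.1.2 and Table 5 footnote 12:** name durvalumab as the permitted agent instead of an example, to match Section 7.1.2.
- **Section 7.4.5:** exempt protocol-permitted durvalumab explicitly and bar any other checkpoint inhibitor during study treatment.
- **Section 13.3:** make direct entry to Phase II conditional on no checkpoint inhibitor being planned, instead of on durvalumab not being chosen.

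The synopsis and Section 7.1 need no substantive change. The general immunotherapy-exposure stratification in Sections 5 and 13.2 should stay. Narrowing it to durvalumab would drop exposure to other agents, which the Rationale gives as a reason for the factor.

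The cost is amendment wording in a handful of places and perhaps the loss of a few candidates on another checkpoint inhibitor. If durvalumab-only was always intended, nothing is lost.
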